7.4 Treatments

The study drug and reference products are manufactured, packaged, and labeled according to Good Manufacturing Practice (GMP) regulations. The Investigational Product should be securely stored under conditions indicated in the IB.

The amount of investigational product administered will be calculated based on a subject's weight (Section 7.4.1). Treatment with oral phosphates and active vitamin D will be individualized to reflect real-world clinical practice, but general guidance will be provided (Section 7.4.2).

Selection of doses, dose titration, and dose adjustments for the investigational product are described in Section 7.4.4.

7.4.1 Investigational Product (KRN23)

KRN23 is a sterile, clear, colorless, and preservative-free solution in single-use 5-mL vials containing 1 mL of KRN23 at a concentration of 10 mg/mL or 30 mg/mL. The starting dose will be 0.8 mg/kg Q2W. The dose may be increased to 1.2 mg/kg at any time during the study if a subject meets the following dose-adjustment criteria: 1) 2 consecutive serum phosphorus measurements are below the normal range; 2) serum phosphorus has increased by ≤ 0.5 mg/dL from baseline; and 3) the subject has not missed a dose of KRN23 that would account for the decrease in serum phosphorus. The maximum allowable dose of KRN23 per administration is 90 mg.

At any time during the study, if serum phosphorus increases above the upper limit of normal (ULN) for age, the subsequent dose(s) will be withheld and the site will contact the medical monitor before dosing resumes. Once other causes of increased serum phosphorus are excluded, KRN23 treatment will resume at half the total dose of the last dose received (ie, half of either 0.8 mg/kg or 1.2 mg/kg; maximum dose per administration: 40 mg). Serum phosphorus will be followed through unscheduled serum phosphorus assessments (approximately 2 weeks post-dose and assessed by the central laboratory; the assessments may be repeated as necessary). A subject will resume dosing at the previous full total dose level if they meet the same dose-adjustment criteria listed above.

Subjects will receive study drug via SC injection to the abdomen, upper arms, thighs, or buttocks; the injection site should be rotated with each injection. If the dose level exceeds 1.5 mL in volume, the dose should be administered at 2 injection sites.

KRN23 dosing should occur no sooner than 8 days after the last dose administered.

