9. For the PROMIS Pediatric Pain Interference, Fatigue, and Physical Function Mobility scales, the parent or legal guardian will complete a Parent/Legal Guardian form for subjects ages 5 to < 8 years of age at the Screening Visit. Subjects ≥ 8 years of age at the Screening Visit will complete a pediatric self-report form. Parent/Legal Guardian forms will be used for the duration of the study for subjects < 8 years of age at the Screening Visit who had a baseline assessment, even when a subject turns 8 during the study. If a subject ≥ 8 years of age at screening has difficulty completing the PROMIS self-report, the investigator may allow the PROMIS interview to be administered by trained clinic staff or allow the parent to complete the PROMIS Parent Proxy version. The reason should be carefully documented and consistent practice of administration should be maintained for every visit from Baseline.
10. If a subject is < 5 years of age at the Screening Visit and therefore has no baseline data, SF-10 will not be administered even when the subject turns 5 during the study.
11. Blood and urine to be collected after a minimum overnight fasting time of 4 hours and prior to drug administration (if applicable). Record fasting duration on CRF. Serum phosphorus may be collected as an unscheduled laboratory assessment if necessary. Details for blood and urine collection can be found in the central laboratory manual.
12. Pre- and post-prandial serum phosphorus and calcium concentrations will be assessed at a single clinic visit anytime 10 to 14 days after a KRN23 dose; this clinic visit may take the place of a Home Health visit. Approximately 20 subjects, age ≥ 3 years, will fast overnight for a minimum of 8 hours, and fasting serum will be collected prior to a breakfast containing predefined ranges of phosphate, calories, and carbohydrate representative of a typical Western diet for children. Serum samples will be drawn 1 and 2 hours after the completion of the meal (refer to Table 7.5.4.3.1).

13. Serum KRN23 concentrations and ADA assessment will be performed only for subjects randomized to KRN23 during the Treatment Period and for all subjects during the Treatment Extension Period. If development of anti-KRN23 antibodies is suspected in a given subject, samples may be obtained at additional time points on a case-by-case basis.

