to Week 40 by 30% ($p=0.0076$) as assessed by the Thatcher Rickets Severity Score (RSS), with greater improvements seen with Q2W dosing (44% reduction; $p=0.0126$) than with Q4W dosing (14% reduction). The greatest improvement was observed in a subset of patients ($n=18$) with clear evidence of rickets at baseline (baseline RSS ≥ 1.5) (59% reduction with Q2W dosing and 47% reduction with Q4W dosing; $p<0.0001$ for both dose groups). Consistency in the rickets results was observed using the Radiographic Global Impression of Change (RGI-C; -3=worsening; +3=complete healing), with rickets improving by +1.56 points ($p<0.0001$) in the Q2W dosing group and by +1.20 points ($p<0.0001$) in the Q4W dosing group at Week 40. In the subgroup with a baseline RSS ≥ 1.5 , RGI-C improved by +2.0 points ($p<0.0001$) in patients who received Q2W dosing, indicating substantial healing of rickets, and by +1.70 ($p<0.0001$) in patients who received Q4W dosing. The 40-week analysis also revealed that the Q4W dosing group showed a peak in serum phosphorus at 2 weeks after dosing followed by a decrease in serum phosphorus levels before the next dose (though remaining above baseline), whereas the Q2W regimen showed stable serum phosphorus levels slowly increasing over time. Overall, the dose-response and PD results observed in the pediatric study were consistent with the adult XLH data generated to date. None of the subjects had serum phosphorus levels above the normal range in either dosing group. Most treatment-related adverse events (AE) were mild, most commonly a transient injection site reaction (39%). One child experienced a serious AE and was hospitalized for fever/muscle pain that improved and continues in the trial. No clinically meaningful changes occurred in serum or urine calcium, serum iPTH, or renal ultrasound.

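### After phosphorus exceeds the age-specific ULN, KRN23 may restart at half dose without a repeat value at or below the ULN

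*Protocol*

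**What the plan says.** Protocol 7.4.1 deals with a phosphorus value above the ULN for age in four steps.

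- **Hold.** At any time in the study, "the subsequent dose(s) will be withheld and the site will contact the medical monitor before dosing resumes".
- **Restart at half dose.** "Once other causes of increased serum phosphorus are excluded, KRN23 treatment will resume at half the total dose of the last dose received", with a cap of 40 mg per administration.
- **Follow-up.** Phosphorus is tracked by unscheduled central-laboratory assessments about 2 weeks post-dose, which may be repeated as needed.
- **Return to full dose.** "A subject will resume dosing at the previous full total dose level if they meet the same dose-adjustment criteria listed above".

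The criteria in the last step are those for raising the dose to 1.2 mg/kg. The first is that "2 consecutive serum phosphorus measurements are below the normal range"; the other two are a rise from baseline of no more than 0.5 mg/dL and no missed dose that would explain the low values.

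The Synopsis and Protocol 7.1 repeat the restart rule, and SAP 3.2 carries the same restart condition.

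**The concern.** Two conditions stand between an above-range value and the next injection: contact with the medical monitor, and exclusion of other causes. Neither is a phosphorus result. If other causes are excluded, KRN23 itself is the likely explanation, and that is the finding on which the text says treatment will resume.

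The hazard is one the protocol names. Section 5.2.2 reports soft-tissue and organ mineralization with prolonged and excessive serum phosphate, nephrocalcinosis at the highest dose tested, and reversibility that could not be established. Re-dosing a child whose phosphorus has not come down lengthens that exposure. The monitor is consulted but is given no level on which to decide.

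**Working it through.** The main check is textual; the arithmetic only sets the scale.

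**1. Phosphorus criteria for KRN23 dosing decisions, side by side**

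- Entry (Protocol 7.3.1, criterion 3): below 3.0 mg/dL.
- First KRN23 dose after crossover (Protocol 7.1): below 3.2 mg/dL, with a retest within a week if not met.
- Increase to 1.2 mg/kg (7.4.1): two consecutive values below normal and a rise of at most 0.5 mg/dL.
- Return to full dose after a reduction (7.4.1): the same criteria.
- Half-dose restart after a high value (7.4.1): no level and no repeat test.

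The restart is the exception in an otherwise explicit scheme.

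**2. Whether another rule supplies a recovery level**

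- Protocol 7.3.3.1 acts on new or worsening mineralization on renal ultrasound.
- Protocol 7.5.3.12 starts a dosing evaluation at a confirmed value of 6.5 mg/dL or more.
- SAP 5.16 calls for case-by-case evaluation when values above the ULN continue despite dose reduction.

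None states a level to be reached before restart. With the SAP 8.5.4.7 normal range of 3.2 to 6.1 mg/dL, the band above the ULN but below the dose-limiting level is 6.5 − 6.1 = 0.4 mg/dL wide.

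**3. Whether scheduled sampling fills the gap**

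Dosing is every 2 weeks. In Table 2.2, phosphorus is scheduled at Weeks 32, 33, 40, 52 and 64, so the later gaps are 40 − 33 = 7 weeks, 52 − 40 = 12 weeks and 64 − 52 = 12 weeks. A scheduled value before restart cannot be relied on. An unscheduled one is possible, but the rule does not make its result a condition.

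**4. How often the rule would be used**

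Protocol 5.2.3 says of the Phase 2 interim analysis (36 children, 40 weeks): "None of the subjects had serum phosphorus levels above the normal range in either dosing group".

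- One-sided 95% upper bound for 0 of 36: 1 − 0.05^(1/36) = 0.0798, or 8.0%.
- Applied to 30 KRN23 children: 0.0798 × 30 = 2.4.

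Distance to the limit: a child entering just below 3.0 mg/dL must rise by about 6.1 − 3.0 = 3.1 mg/dL to reach the SAP upper limit. The mean Phase 2 rise at about 0.8 mg/kg every 2 weeks was 0.7 mg/dL (Protocol 7.2), and 3.1 / 0.7 = 4.4.

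These figures describe any exceedance. The documents do not say what share of such children would still be above range at restart, so none is estimated here.

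**The case against.** The strongest reply is that the rule already holds the drug whenever phosphorus is above the ULN, at any time. A repeat value that is still high can fairly be read as meeting the hold again. The hold covers one or more doses, so it is open-ended. The monitor must be contacted, and a sensible monitor would probably wait. The assessments are plural and repeatable, and those about 2 weeks post-dose may be counted from the last dose before the hold, which would put a result in hand before restart. Half dose and the 40 mg cap limit exposure. Protocol 7.5.3 also refers to a Study Reference Manual, not available here, which may contain retest instructions.

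Much of this stands, and it narrows the point. What remains is that the protocol requires no repeat test before restart and ties restart to no result, on either reading of post-dose.

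Three stronger readings are tempting, and the documents support none of them.

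- A reader might infer that restart depends solely on excluding other causes. Contact with the monitor is also mandatory.
- A reader might infer that nothing else protects a child below 6.5 mg/dL. Adverse-event recording (7.5.3.13), removal for an unacceptable event (7.3.3) and data monitoring committee review (8.5.6) also apply, although none sets a restart level.
- A reader might take the reference to half of 0.8 or 1.2 mg/kg to cover only a first exceedance. It fits any exceedance at full dose, including one after return to full dose.

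**Conclusion.** The gap is real but small. As written, KRN23 may resume at half dose after monitor contact and exclusion of other causes, with no repeat phosphorus and no requirement that the value be at or below the age-specific ULN. It is a minor safety correction and affects no planned analysis.

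The expected frequency is low, but the Phase 2 figure is only a guide. It pools two dosing intervals over 40 weeks. Its doses reached 2.0 mg/kg, above the 1.2 mg/kg level here, which suggests fewer exceedances in this trial. Against that, Phase 2 enrolled ages 5 to 12, while about 10 of the 30 KRN23 children here (33%) are under 5. Treatment lasts up to 140 weeks, and control children outside Japan and Korea may cross over to KRN23, so more than 30 may be exposed. The distance-to-limit comparison rests on one SAP range and a mean rise; age-specific limits and individual responses will differ.

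**What to change.** Replace the restart sentence in Protocol 7.4.1, and its copies in the Synopsis and 7.1, with wording such as:

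*KRN23 stays on hold until the medical monitor has been contacted, other causes have been excluded, and a repeat serum phosphorus is at or below the age-specific ULN. It then restarts at half the last administered dose, to a maximum of 40 mg per administration.*

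Keep the cap: half of the 90 mg maximum dose is 45 mg, so it has effect.

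No new procedure is needed. Footnote 11 to the Schedule of Events already states: "Serum phosphorus may be collected as an unscheduled laboratory assessment if necessary". If central turnaround would delay dosing, the Week 66 crossover arrangement (same-day local result with a parallel central sample) is a ready model.

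The cost is one extra sample, and possibly a longer hold, in the few children affected.

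Optionally, carry the SAP 5.16 provision on continued values above the ULN despite dose reduction into Protocol 7.5.3.12. SAP Section 3 treats the protocol as the definitive reference, so that is where sites would look.

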7.4.2 Active Control (Reference) Therapy

The study is designed as an open-label comparison with oral phosphate and active vitamin D therapy, which will be individualized by subject at the investigator's discretion based on published US and European expert guidelines (Carpenter et al. 2011), (Linglart et al. 2014) (in Table 7.1.1 and Table 7.1.2). It should be noted that while commonly used, oral phosphate and active vitamin D therapy are not approved for the treatment of XLH.

Detailed information about the brand, starting dosages, and any changes in oral phosphate and active vitamin D therapy will be determined by the treating Investigator within the expert guidelines and recorded at every site visit. US expert guidelines generally recommend a calcitriol dosage of 20 to 30 ng/kg/day in 2 to 3 divided doses and an elemental phosphorus dose of 20 to 40 mg/kg/day (in 3 to 5 divided doses), acknowledging that some children require more, whereas some do well with less (Carpenter et al. 2011). European expert guidelines recommend an alfacalcidol dosage of 1 to 2 µg/day (once daily) and a phosphate supplemental dose of 45 to 70 mg/kg/day (in 3 to 4 divided doses) (Linglart et al. 2014). Calcitriol and alfacalcidol dosages should be adjusted based on the clinical and laboratory values that guide best possible treatment.

7.4.3 Method of Assigning Subjects to Treatment Groups

Eligible subjects will be enrolled in the study and sequentially assigned an identification number. Subjects will be randomized 1:1 to receive open-label KRN23 by subcutaneous injection or active control via an Interactive Web Response System (IWRS) based on a randomization schedule developed by an independent third-party vendor. Randomization will be stratified by baseline rickets severity (RSS total score ≤ 2.5 vs > 2.5) and age (< 5 vs ≥ 5 years).

After completion of the 64-week Treatment Period, subjects in Europe, the US, Canada, and Australia who were randomized to KRN23 will continue treatment with KRN23 at their previous dose and regimen in the Treatment Extension Period. Subjects in Europe, the US, Canada, and Australia who were randomized to active control will cross over to receive KRN23 at the starting dose and regimen administered to subjects in the KRN23 arm (starting dose of 0.8 mg/kg Q2W; dose may be increased to 1.2 mg/kg Q2W).

7.4.4 Selection of Doses and Study Duration

The amount of KRN23 administered will be calculated based on the subject's weight. As discussed earlier, data from the pediatric Phase 2 study suggested KRN23, administered Q2W at approximately 0.8 mg/kg for 40 weeks, increased serum phosphorus by an average of 0.7 mg/dL; increases of > 0.5 mg/dL were seen in 83.3% of subjects. The Q2W dosing regimen was chosen for this Phase 3 study because it appeared to produce a more stable and consistent increase in serum phosphorus levels with less fluctuation over time than the every 4 week (Q4W) dosing regimen, and a safety profile that was not substantially different from the Q4W dosing regimen.

The duration of treatment is intended to define whether KRN23 is safe for long-term use and provide sufficient insight on sustained clinical effects and improvements in rickets and active bone disease in pediatric XLH patients. A study duration of 40 weeks, similar to the Phase 2 study (UX023-CL201), is considered sufficient to observe treatment effect on rickets; therefore, the primary analysis was established at Week 40. A longer period of 64 weeks will assess the durability of treatment effect, additional efficacy outcomes, and long-term safety. The Treatment Extension Period will provide long-term safety and efficacy data up to 140 weeks.

Treatment duration will vary by region. The study consists of a Treatment Period (64 weeks) for all subjects and a Treatment Extension Period (up to 76 weeks) for subjects in Europe, the US, Canada, and Australia. For subjects in Japan and Korea, the planned duration of treatment in this study is 64 weeks, and the Week 64 visit at the end of the Treatment Period will be the EOS I visit. For subjects in Europe, the US, Canada, and Australia, the planned duration of treatment is up to 140 weeks (64 weeks in the Treatment Period and up to 76 weeks in the Treatment Extension period). In Europe and Australia, treatment in the Treatment Extension Period will end by September 2018, and subjects will be enrolled in separate clinical trials of KRN23 or will receive KRN23 through another mechanism. In the US and Canada, treatment in the Treatment Extension Period will end by September 2018 or June 2019, respectively (expected availability of commercial KRN23); subjects will receive commercial KRN23 or will receive KRN23 through another mechanism. The duration of Treatment Extension Period will vary for individual subjects and will be determined by the time from Week 64 through the EOS II visit.

The end of the study for reporting purposes is defined as the date of the last protocol-specified procedures (including telephone contact) for the last subject in the study.

7.4.5 Prior and Concomitant Therapy

Throughout the study, there should be no significant changes to a subject's diet or medication schedule unless medically indicated. Investigators may prescribe any concomitant medications or treatments deemed necessary to provide adequate supportive care, except those listed in Section 7.4.5.1. All concomitant medications taken during the study will be recorded in the CRF with indication, dose information, and dates of administration. Any changes to concomitant medication will also be documented.

7.4.5.1 Prohibited Medications

To be eligible for the study, all subjects will undergo a washout period where they will discontinue treatment with oral phosphates and pharmacologic vitamin D metabolites or analogs (eg, calcitriol, doxercalciferol, alfacalcidol, and paricalcitol) for 7 days prior to randomization. Eligible subjects will then be randomly assigned to receive either KRN23 treatment or oral phosphates/active vitamin D treatment (control). Subjects randomly assigned to KRN23 are prohibited from receiving oral phosphates and active vitamin D for

the duration of the study. Subjects randomly assigned to the active control arm will be permitted to receive oral phosphates/active vitamin D treatment after randomization.

At Week 64 for subjects continuing into the Treatment Extension Period, subjects randomized to active control in the Treatment Period will cross over to receive KRN23 at the dose and regimen administered to subjects in the KRN23 arm. Active control will be discontinued after the Week 64 visit to allow washout of oral phosphate and active vitamin D treatments before the first dose of KRN23 at Week 66.

In addition, subjects must agree to discontinue use of certain medications for the indicated timeframe to qualify for study entry (Section 7.3).

- Growth hormone therapy within 12 months before the Screening Visit
- Aluminum hydroxide antacids (eg, Maalox[®] and Mylanta[®]), systemic corticosteroids, acetazolamide, and thiazides within 7 days prior to the Screening Visit
- Current and prior use of leuporelin (eg, Lupron[®], Viadur[®], Eligard[®]), triptorelin (TRELSTAR[®]), goserelin (Zoladex[®]), or other drugs known to delay puberty
- PTH suppressors (eg, Sensipar[®], cinacalcet, calcimimetics) within 2 months prior to the Screening Visit
- Any therapeutic mAb therapy within 90 days prior to the Screening Visit

NOTE: Oral phosphate treatment must be down-titrated slowly to avoid hypercalciuria. Vitamin D metabolites or analogs may be discontinued without titration.

7.4.5.2 Permitted Medications

Other than the medications specifically prohibited in this protocol, subjects may receive concomitant medications as required. Subjects randomly assigned to the active control arm may receive oral phosphate/active vitamin D treatment after a 7-day washout and randomization. If serum 25-hydroxyvitamin D (25(OH)D) levels fall below 16 ng/mL, oral supplementation may be provided. Medications (investigational, prescription, over-the-counter, and herbal) and nutritional supplements taken during the 30 days prior to Screening Visit will be reviewed and recorded.

7.4.6 Treatment Compliance

Trained personnel will administer KRN23 by SC injection or dispense oral phosphates and active vitamin D treatment at the investigational site or during home health visits (KRN23 treatment arm only) as indicated in the Schedule of Events (Table 2.1 Table 2.2, and Table 2.3). Each administration of study drug or oral phosphate/active vitamin D (including type, dose, and frequency) will be recorded on the CRF. If a subject does not receive a dose within 10 days of a scheduled dose for the Q2W regimen of study drug, that dose should be skipped and the next dose will be administered at the next scheduled Q2W dosing visit.

7.5 Study Procedures and Assessments

7.5.1 Schedule of Events

The schedule of visits and assessments are provided in [Table 2.1](#) and [Table 2.2](#), and [Table 2.3](#). Home Health visits (KRN23 treatment arm only) may be conducted at the investigational site depending on the preference of the subject and proximity of the subject to the clinic. Refer to the Study Reference Manual for additional details and a recommended schedule of specific assessments.

Potential subjects will come in to the site for an initial Screening Visit and provide informed consent. All subjects will have x-rays (knees and hand/wrist) at the Screening Visit and confirmed by central read prior the Baseline visit to determine if the subject meets the eligibility criteria. If radiographic evidence of rickets is not present (ie, RSS total score ≥ 2.0), the subject will be considered a screen failure. Patients with confirmed rickets who also have a *PHEX* mutation or variant of uncertain significance in either self or an appropriate directly related family member can start the process of weaning from oral phosphate/active vitamin D therapy (Section [7.4.5.1](#)) and return to the site after 7 days for the Baseline visit if all other inclusion criteria are met. *PHEX* mutation analysis will be performed in all subjects. Potential subjects without a previously confirmed *PHEX* mutation will be notified of *PHEX* mutation results, and if presence of a mutation is confirmed, will have the baseline visit scheduled.

Subjects who successfully pass the requirements at the Screening Visit will discontinue oral phosphate for a minimum of 7 days and active vitamin D therapy for a minimum of 7 days prior to the Baseline visit. The Screening Visit window may be up to 8 weeks for *PHEX* mutation analysis and washout of oral phosphate and active vitamin D therapy. Subjects who have serum 25(OH)D below the lower limit of normal (16 ng/mL) will need to have the levels corrected and, assuming they meet all other eligibility requirements, the subject may be rescreened after a minimum of 7 days. Walking ability (6MWT; for subjects ≥ 5 years of age at the Screening Visit) will be completed at the Screening Visit (for practice) and at the Baseline (Week 0) visit; the Baseline 6MWT must be assessed on the same day that the questionnaires are administered. Pain, fatigue, and physical function (PROMIS [Patient-Reported Outcomes Measurement Information System] Pain Interference, Physical Function Mobility and Fatigue domain scores; for subjects ≥ 5 years of age at the Screening Visit); pain intensity (Faces Pain Scale – Revised [FPS-R] for subjects ≥ 5 years of age at the Screening Visit, and the SF-10 for Children Health Survey (SF-10; for subjects ≥ 5 years of age at the Screening Visit) may be completed at the Baseline visit.

Historical radiographs of the anteroposterior (AP) knee, posteroanterior (PA) hand/wrist, and long leg are of importance and interest to evaluate the presentation and severity of the subject's XLH disease and rickets severity over time. Available AP knee, PA hand/wrist, and standing long leg radiographs taken in the 5 years prior to the Screening Visit will be collected; radiographs of other skeletal locations will not be collected. Approximately 1 set of radiographs per year will be collected; if there are multiple sets within a year, the set

closest to the subject's birthday should be obtained. The wrist and knee radiographs will be used to evaluate rickets severity and to determine how much rickets fluctuate over time in patients who were treated with oral phosphate/active vitamin D prior to study enrollment. The standing long leg radiographs will be used to assess changes in genu varum and/or valgum following prolonged treatment with oral phosphate/active vitamin D prior to study enrollment. The images will be de-identified and rated using the RSS and RGI-C.

Similarly, historical growth data are of importance and interest. All available recumbent length and standing height data assessed prior to the Screening visit will be collected.

All study visits will be scheduled relative to the Baseline visit, with an allowable variance of ± 3 days for each visit (with the exception of the Screening and Safety Follow-up Visits) to accommodate scheduling. All Screening/Baseline assessments and inclusion/exclusion criteria based on central laboratory results must be satisfied prior to randomization and dosing. KRN23 dosing should occur no sooner than 8 days since the last dose administered.

Subjects may be monitored between site visits through a series of Home Health visits (KRN23 treatment arm only) depending on the preference of the subject and the proximity of the subject to the site. Home Health visits are not applicable to subjects in Japan or Korea. The visit window for Home Health visits is ± 3 days during the Treatment Period. HH visits are not required for subjects randomized to the active control arm because they do not require their medicine to be administered by a healthcare professional. To more closely mimic clinical practice, subjects randomized to the active control arm will only be seen at the site visits. For subjects who discontinue prior to completing the study, every reasonable effort should be made to perform the Early Termination visit procedures within 4 weeks of discontinuation. X-rays will not be performed at the Early Termination visit if post-treatment test(s) have been performed within 6 months of Early Termination. Similarly, the 6MWT will not be performed at the Early Termination visit if post-treatment test(s) have been performed within 3 months of Early Termination or if Early Termination occurs after Week 64.

Post-study safety follow-up calls and safety visits will occur only for subjects who are not documented to be continuing on KRN23 at the Week 64/EOS I Visit or EOS II Visit, as appropriate. A safety follow-up telephone call will occur for these subjects at 5 weeks (+5 days) after the Week 64/EOS I visit (in Japan and Korea) or after the EOS II visit (in Europe, the US, Canada, and Australia) to determine if the subject is receiving KRN23 therapy in another clinical trial, as commercial product, or through another mechanism. If KRN23 therapy has not been started, information on any ongoing or new AEs, SAEs, or concomitant medications will be collected. For subjects who do not continue KRN23 therapy, an additional safety visit will occur 12 weeks ± 1 week after the last dose of study drug. Every reasonable effort should be made to have required subjects return to the clinic for the final safety visit; however, subjects who are unable to return to the clinic for the final safety visit will be given the option of providing blood and urine samples as part of a Home Health visit.

The end of the study is defined as the date of the last protocol-specified procedures (including telephone contact) for the last subject in the study.

